### **3.2 EXCLUSION CRITERIA**

Subjects meeting any of the following criteria will be excluded from the study:

1. Subject is a female who is pregnant or breastfeeding or planning to become pregnant within 3 months after the last dose of study drug.
2. Subject has a history of any clinically significant conditions including:
  - Asthma treated with oral systemic steroids within the past 6 months
  - Diabetes mellitus (type 1 or 2), with the exception of gestational diabetes
  - Thyroidectomy or thyroid disease that required medication within the past 12 months
  - Serious angioedema episodes within the previous 3 years or requiring medication in the previous 2 years
  - Head trauma resulting in a diagnosis of traumatic brain injury other than concussion
  - Frequent episodes of headache.
3. Subject has received treatment in another clinical study of an investigational drug (or medical device) within 30 days or 5 half-lives (whichever is longer) before the first dose of study drug.
4. Subject has been previously enrolled in any clinical study involving TPOXX (tecovirimat).
5. Subject has a history of relevant drug and/or food allergies (ie, allergy to tecovirimat or excipients, or any significant food allergy that could preclude a standard diet in the study site).
6. Subject has any condition possibly affecting drug absorption (eg, previous surgery on the gastrointestinal tract, including removal of parts of the stomach, bowel, liver, gallbladder, or pancreas, with the exception of appendectomy).
7. Subject has evidence or history of clinically significant allergic (except for untreated, asymptomatic, seasonal allergies at time of the first dose of study drug), hematological, endocrine, pulmonary, gastrointestinal, cardiovascular, hepatic, psychiatric, or neurological disease. Exceptions to these criteria (eg, stable, mild

- joint disease unassociated with collagen vascular disease) may be made following discussions with the medical monitor.
8. Subject has a history of cardiac disease, symptomatic or asymptomatic arrhythmias, syncopal episodes, or risk factors for torsades de pointes (eg, heart failure, hypokalemia).
  9. Subject has a family history of sudden cardiac death not clearly due to acute myocardial infarction.
  10. Subject has a seizure disorder or history of seizures (does not include childhood febrile seizures) or a past history that increases seizure risks such as significant head injury that caused loss of consciousness or other changes in the subject's daily function, concussion, stroke, central nervous system infection or disease, or alcohol or drug abuse or family history of idiopathic seizures.
  11. Subject has a history of a peptic ulcer or significant gastrointestinal bleed.
  12. Subject has a bleeding disorder diagnosed by a doctor (eg, factor deficiency, coagulopathy, or platelet disorder requiring special precautions) or significant bruising or bleeding difficulties with blood draws.
  13. Subject has a malignancy that is active, or treated malignancy for which there is not reasonable assurance of sustained cure, or malignancy that is likely to recur during the period of the study (subject should be in complete remission for at least 5 years).
  14. Subject has neutropenia or other blood dyscrasia determined to be clinically significant by the investigator.
  15. Subject has used any of the following prohibited medications from within 7 days (or 5 half-lives, whichever is longer) before the first dose of study drug: antidiabetic medication; anticoagulants; anticonvulsants; substrates of the BCRP transporter including methotrexate, mitoxantrone, imatinib, irinotecan, lapatinib, rosuvastatin, sulfasalazine, and topotecan; substrates of CYP2C8 including repaglinide, paclitaxel, Montelukast, pioglitazone, rosiglitazone; and substrates of CYP2C19 including S-mephenytoin, clobazam, diazepam, rabeprazole, voriconazole, lansoprazole, and omeprazole. Medications not listed here that are known (or thought) to be CYP3A4 substrates may be allowed at the investigator's discretion, after consultation with the medical monitor, if administration poses little to no risk to the subject.

16. Subject has a history of drug or alcohol abuse or dependency within the last year before screening.
17. Subject has a history of an eating disorder.
18. Subject has a current or recent (<30 days before screening) history of clinically significant bacterial, fungal, or mycobacterial infection.
19. Subject has a current clinically significant viral infection.
20. Subject has a known clinically significant chronic viral infection (eg, human T cell lymphotropic virus I or II).
21. Subject has consumed grapefruit or grapefruit juice, Seville orange or Seville orange-containing products (eg, marmalade), or caffeine- or xanthine-containing products within 48 hours before the first dose of study drug or throughout the study.
22. Subject has used any prescription (excluding hormonal birth control) or over-the-counter medication (including herbal or nutritional supplements) within 14 days before the first dose of study drug.
23. Subject demonstrates long-term use ( $\geq 14$  consecutive days) of glucocorticoids including oral or parenteral prednisone or equivalent ( $> 20$  mg total dose per day) or high-dose inhaled steroids ( $> 800$  mcg/day of beclomethasone dipropionate or equivalent) within the preceding 1 month (low-dose [ $\leq 800$  mcg/day of beclomethasone dipropionate or equivalent] inhaled and topical steroids are allowed).
24. Subject has donated  $> 450$  mL blood or blood components within 30 days before the first dose of study drug. The investigator should instruct subjects who participate in this study to not donate blood or blood components for 4 weeks after the completion of the study.
25. Subject is a smoker or has used nicotine or nicotine-containing products (eg, cigarettes, electronic vapor cigarettes, cigars, chewing tobacco, snuff, nicotine patches, or nicotine gum) within 6 months before the first dose of study drug.
26. Subject has consumed pomegranate or pomegranate juice, pomelo fruits or pomelo juice, or alcohol within 72 hours before the first dose of study drug.
27. Subject reports participation in strenuous activity or contact sports within 24 hours before the first dose of study drug.

28. Subject has known hepatitis B or C infection or positive test for hepatitis B surface antigen, hepatitis C virus antibody, or human immunodeficiency virus type 1 or 2 antibodies at screening.
29. Subject has a positive test result for amphetamines (including methamphetamines and ecstasy/methylenedioxymethamphetamine), barbiturates, benzodiazepines, cannabinoids (including tetrahydrocannabinol), cocaine metabolites, opiates (including heroin, codeine, and oxycodone), or alcohol at screening or check-in.
30. Subject has any of the following laboratory test results within 28 days before the first dose of study drug:
  - Estimated serum creatinine clearance (Cockcroft-Gault) <90 mL/min
  - Creatinine in males >1.7 mg/dL and in females >1.4 mg/dL (1.3 times the upper central laboratory reference range)
  - Hemoglobin ≤10% of the lower central laboratory reference range
  - White blood cell count not within the central laboratory reference range
  - Absolute neutrophil count <1000 cells/mm^3
  - Platelets not within ±10% of central laboratory reference range
  - Alanine aminotransferase >1.5 times above the upper central laboratory reference range
  - Aspartate aminotransferase >1.5 times above the upper central laboratory reference range
  - Alkaline phosphatase >20% above the upper central laboratory reference range
  - Hemoglobin A1c ≥7.0%
  - Cholesterol ≥300 mg/dL and low-density lipoprotein ≥190 mg/dL.
31. Subject has a blood pressure considered to be clinically significant by the investigator. Blood pressure may be retested twice in the sitting position at 5-minute intervals.
32. Subject has a resting heart rate of <40 beats per minute or >100 beats per minute at screening.
33. Subject has an abnormal ECG at screening that is determined by the investigator to be clinically significant.
34. Male subject has a QTcF >450 ms or female subject has a QTcF >470 ms at screening or Day -1.
35. In the opinion of the investigator, the subject is not suitable for entry into the study.

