21. Subject has consumed grapefruit or grapefruit juice, Seville orange or Seville orange-containing products (eg, marmalade), or caffeine- or xanthine-containing products within 48 hours before the first dose of study drug or throughout the study.
22. Subject has used any prescription (excluding hormonal birth control) or over-the-counter medication (including herbal or nutritional supplements) within 14 days before the first dose of study drug.

23. Subject demonstrates long-term use ( $\geq 14$  consecutive days) of glucocorticoids including oral or parenteral prednisone or equivalent ( $>20$  mg total dose per day) or high-dose inhaled steroids ( $>800$  mcg/day of beclomethasone dipropionate or equivalent) within the preceding 1 month (low-dose [ $\leq 800$  mcg/day of beclomethasone dipropionate or equivalent] inhaled and topical steroids are allowed).
24. Subject has donated  $>450$  mL blood or blood components within 30 days before the first dose of study drug. The investigator should instruct subjects who participate in this study to not donate blood or blood components for 4 weeks after the completion of the study.
25. Subject is a smoker or has used nicotine or nicotine-containing products (eg, cigarettes, electronic vapor cigarettes, cigars, chewing tobacco, snuff, nicotine patches, or nicotine gum) within 6 months before the first dose of study drug.
26. Subject has consumed pomegranate or pomegranate juice, pomelo fruits or pomelo juice, or alcohol within 72 hours before the first dose of study drug.
27. Subject reports participation in strenuous activity or contact sports within 24 hours before the first dose of study drug.
28. Subject has known hepatitis B or C infection or positive test for hepatitis B surface antigen, hepatitis C virus antibody, or human immunodeficiency virus type 1 or 2 antibodies at screening.
29. Subject has a positive test result for amphetamines (including methamphetamines and ecstasy/methylenedioxymethamphetamine), barbiturates, benzodiazepines, cannabinoids (including tetrahydrocannabinol), cocaine metabolites, opiates (including heroin, codeine, and oxycodone), or alcohol at screening or check-in.
30. Subject has any of the following laboratory test results within 28 days before the first dose of study drug:
  - Estimated serum creatinine clearance (Cockcroft-Gault)  $<90$  mL/min
  - Creatinine in males  $>1.7$  mg/dL and in females  $>1.4$  mg/dL (1.3 times the upper central laboratory reference range)

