## 6.2.2 Clinical Laboratory Testing

Clinical laboratory tests will be performed by the PPD Central Laboratory. Blood samples will be collected at the time points indicated in the schedule of events (Table 9-1) and will be prepared using standard procedures.

Repeat clinical laboratory tests may be performed at the discretion of the investigator, if necessary, to evaluate inclusion and exclusion criteria or clinical laboratory abnormalities. PPD central laboratory will provide the reference ranges for all clinical laboratory safety parameters.

The following clinical laboratory assessments will be performed:

Hematology	Hematocrit, hemoglobin, mean corpuscular hemoglobin, mean corpuscular hemoglobin concentration, total and differential leukocyte count (basophils, eosinophils, lymphocytes, monocytes, neutrophils), mean corpuscular volume, platelet count, red blood cell count, and red cell distribution width
Serum Chemistry	Alanine aminotransferase, albumin, alkaline phosphatase, anion gap, aspartate aminotransferase, bilirubin (total), blood urea nitrogen, calcium, carbon dioxide, chloride, creatinine clearance (calculated a ), gamma-glutamyltransferase, globulin, glucose, lactate dehydrogenase, phosphorus, potassium, sodium, total protein, and uric acid

Urinalysis                      Appearance, bilirubin, blood, color, glucose, ketones, leukocytes, microscopy (performed if dipstick is  $\geq 1+$ ; includes bacteria, cast, crystals, epithelial cells, red blood cells, and white blood cells), nitrates, pH, protein, specific gravity, turbidity, and urobilinogen

a Creatinine clearance (CLcr) will be calculated using the Cockcroft-Gault formula:

$$CLcr (mL/min) = \frac{[140 - age(years)] \times weight (kg)}{72 \times serum\ creatinine (mg/dL)} \{ \times 0.85 \text{ if female} \}$$

Glycosylated hemoglobin A1c and a fasting lipid panel including cholesterol (total, high-density lipoprotein, calculated low-density lipoprotein, and triglycerides) will be performed at screening.

Serum pregnancy test ( $\beta$  human chorionic gonadotropin) for women of childbearing potential will be performed at screening and on Day -1.

A serum follicle-stimulating hormone test for postmenopausal women will be performed at screening.

Human immunodeficiency virus (type 1 and 2) antibodies, hepatitis B surface antigen, and hepatitis C virus antibody will be assessed at screening only.

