A urine drug screen for alcohol, amphetamines (including methamphetamines and ecstasy/methylenedioxymethamphetamine), barbiturates, benzodiazepines, cannabinoids (including tetrahydrocannabinol), cocaine metabolites, and opiates (including heroin, codeine, and oxycodone) will be performed at screening and on Day -1.

Abnormal clinical laboratory values will be flagged as either high or low (or normal or abnormal) based on the reference ranges for each laboratory parameter. The investigator will determine whether any of the abnormally high or low results are clinically significant or not clinically significant. Clinical significance is defined as any variation in results that has medical relevance and may result in an alteration in medical care (eg, active observation, diagnostic measures, or therapeutic measures). If a clinically significant change from the screening value is noted, the clinically significant value and reason for clinical significance will be documented on the AE page of the eCRF. The investigator will continue to monitor the subject with additional assessments until the values have reached the reference range or the values at screening or until the investigator determines that follow-up is no longer medically necessary.

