### **6.2.6 Physical Examinations**

A full physical examination will be performed at the time points indicated in the schedule of events (Table 9-1) and will include assessment of the following body systems: head, ears, eyes, nose, and throat; cardiac (including auscultation of heart); pulmonary (chest) auscultation of lungs; abdomen; skin; musculoskeletal system; lymphatic system; and neurologic system (cranial nerves, sensation, motor function, coordination, reflexes, and mental status).

A symptom-directed physical examination will be performed at the time points indicated in the schedule of events (Table 9-1) (for those subjects who require it), and at unscheduled visits as necessary. This examination will include an assessment of the heart, lungs, abdomen, a neurologic review, and a review of symptoms for assessments and/or follow-up of reported or potential AEs.

Weight will be measured without shoes and in light clothing at screening and without shoes and in hospital gowns at all other time points indicated in the schedule of events (Table 9-1). The scales should be calibrated, and the same weight scale should be used throughout the study starting with Screening through Day 9. Weight measurements will be rounded to one decimal place.

Height will be measured at Check-in on Day -1.

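### Does it matter that the creatinine-clearance exclusion adds almost nothing to the creatinine limits above 120 kg, and that serum creatinine is not named in the chemistry list?

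*Protocol*

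**What the plan says.** Criterion 30 in Protocol 3.2, repeated in the synopsis, opens with "Subject has any of the following laboratory test results within 28 days before the first dose of study drug", so one listed result is enough to exclude. Two of its bullets are renal: "Estimated serum creatinine clearance (Cockcroft-Gault) <90 mL/min" and "Creatinine in males >1.7 mg/dL and in females >1.4 mg/dL (1.3 times the upper central laboratory reference range"). Inclusion criteria 1 and 2 restrict entry to ages 18 to 50 and to weights above 120 kg at screening, at check-in and before dosing on Day 1.

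Section 6.2.2 states that "Creatinine clearance (CLcr) will be calculated using the Cockcroft-Gault formula". The formula has weight in kg in the numerator, serum creatinine in mg/dL in the denominator, and a factor of 0.85 for women. The serum chemistry row contains "blood urea nitrogen, calcium, carbon dioxide, chloride, creatinine clearance", marked as calculated, and has no separate entry for serum creatinine. The same section has abnormal values flagged "based on the reference ranges for each laboratory parameter". On weight, 6.2.6 says: "Weight will be measured without shoes and in light clothing at screening and without shoes and in hospital gowns at all other time points".

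**The concern.** Three things look untidy together.

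- **Overlap.** A reader who sees a clearance limit of 90 mL/min would take it for an independent renal screen. Cockcroft-Gault clearance rises in proportion to weight, and this trial enrols only very heavy subjects, so the limit may hardly ever act. The creatinine cut-off would then be the only effective numeric screen.
- **Listing.** The analyte that does the screening is not named among the chemistry tests, although its limit is defined as a multiple of a reference range and results are flagged against such ranges.
- **Weight.** The formula does not say which measured weight to use, and weights are taken under two clothing conditions.

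If these were real faults, subjects might be screened differently from what the criterion suggests, or creatinine might go unreported.

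**Working it through.** **Inputs.** Limits of 90 mL/min, 1.7 mg/dL (men) and 1.4 mg/dL (women) from criterion 30; ages 18 to 50 and weight above 120 kg from 3.1; the formula from 6.2.2:

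CLcr = (140 − age) × weight / (72 × Scr), × 0.85 if female, where Scr is serum creatinine.

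The protocol states no derived figure to reproduce here, so the check applies its formula to its own limits.

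**Clearance at the creatinine limit in the most exposed eligible subject (age 50, 120.1 kg).**

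- Man: 90 × 120.1 / (72 × 1.7) = 10,809 / 122.4 = 88.3 mL/min.
- Woman: 90 × 120.1 × 0.85 / (72 × 1.4) = 9,187.65 / 100.8 = 91.1 mL/min.

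Clearance is higher at any lower age, higher weight or lower creatinine. A woman who passes the creatinine limit therefore always passes the clearance limit.

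**Weight below which the clearance limit adds an exclusion.** Setting CLcr = 90 and solving for weight:

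| Sex, creatinine | Age | Weight giving CLcr = 90 | Possible above 120 kg? |
|---|---|---|---|
| Man, 1.7 | 50 | 90 × 72 × 1.7 / 90 = 122.40 kg | yes |
| Man, 1.7 | 49 | 11,016 / 91 = 121.05 kg | yes |
| Man, 1.7 | 48 | 11,016 / 92 = 119.74 kg | no |
| Woman, 1.4 | 50 | 90 × 72 × 1.4 / (90 × 0.85) = 118.59 kg | no |

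The lowest creatinine at which the clearance limit can act in a 50-year-old man at 120 kg is 90 × 120 / (72 × 90) = 1.667 mg/dL. The added exclusions are therefore men aged 50 at 120.1 to 122.3 kg with creatinine 1.67 to 1.70, and men aged 49 at 120.1 to 121.0 kg with creatinine 1.69 to 1.70.

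**Size on a grid.** Take whole-year ages (33 values) and weights from 120.1 to 180.0 kg in 0.1 kg steps (600 values; the 180 kg ceiling is an assumption). That gives 33 × 600 = 19,800 combinations per sex. The clearance limit can add an exclusion in 23 (age 50) + 10 (age 49) = 33 of them for men, or 0.17%, and in none for women. The count of 33 does not depend on the ceiling; the percentage does (with a 200 kg ceiling it is 33 / 26,400 = 0.125%). These are shares of grid cells, not of patients.

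**A more central case (age 35, 150 kg).** Clearance at the creatinine limit is 105 × 150 / (72 × 1.7) = 128.7 mL/min for a man and 105 × 150 × 0.85 / (72 × 1.4) = 132.8 for a woman. Clearance reaches 90 only at creatinine 2.43 or 2.07 mg/dL, which is 1.43 and 1.48 times the creatinine limits.

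**The nesting runs one way.** A man aged 30 at 130 kg with creatinine 1.8 has clearance 110 × 130 / (72 × 1.8) = 110.3 mL/min and is excluded by creatinine alone.

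**Which measured weight.** In a 50-year-old man with creatinine 1.667, 1 kg shifts clearance by 90 / (72 × 1.667) = 0.75 mL/min. Inclusion criterion 2 requires more than 120 kg at screening, check-in and Day 1, so whichever of these weights is used, the answer can differ only in the strip of men described above.

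**Is creatinine measured?** The footnote to the clearance entry divides by serum creatinine, and criterion 30 limits it directly. The listed clearance cannot be produced without the value. A reference range must also exist, since the creatinine limit is expressed as a multiple of it.

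**The case for a change.** The best case for a change is that it costs only words. The protocol, not the SAP, fixes eligibility and laboratory panels, and the analyte carrying the effective limit ought to be a named parameter. In addition, weight is not qualified as actual, ideal or adjusted. If a much lower weight were entered (60 to 90 kg, an assumed range that is not in the protocol), a 40-year-old man would reach clearance 90 at creatinine 100 × 60 / 6,480 = 0.93 to 100 × 90 / 6,480 = 1.39 mg/dL. The clearance limit would then do real work.

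The listing point stands, as an editorial one. The point about weight type does not. Unqualified weight in the standard formula means measured weight, and 6.2.6 takes height only at check-in on Day -1, so no ideal or adjusted weight can be derived from protocol measurements when screening results are assessed. The overlap is real, but the two limits are alternatives. The clearance limit catches the few men the creatinine limit misses, and the creatinine limit catches everyone else with low clearance. Nobody is wrongly admitted or excluded, and acknowledging the overlap would change no decision at the site.

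**Conclusion.** No change is needed. The overlap is nearly complete: no additional woman is excluded, and among men only those aged 49 or 50, below about 122.4 kg, with creatinine of about 1.67 to 1.70 mg/dL. It is harmless because any single result excludes. The missing list entry is a clerical slip that the laboratory and site will fill correctly, since the protocol uses the value in two other places. It could be tidied if 6.2.2 is opened for another reason, but does not justify an amendment. The choice of measured weight is worth about 0.75 mL/min per kg and could matter only in that same group of men.

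This rests on measured body weight entering the formula, age taken in whole years, and the printed limits of 1.7 and 1.4 mg/dL. The laboratory's reference ranges are not given, so the multiple of 1.3 cannot be checked. The arithmetic describes possible subjects, not how many will present, and gives no reason to expect any effect on the pharmacokinetic or safety results.

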### **3.3 OTHER SCREENING CONSIDERATIONS**

#### **3.3.1 Subject Restrictions During the Study**

- Subjects must be willing to remain confined at the study site from check-in (Day –1) until safety assessments are completed on Day 9.
- Subjects who have abnormal physical examination findings or an ongoing AE/SAE on Day 9 that is deemed related to study drug or per investigator or SIGA discretion will return to the study site on Day 14 (+2 days) for a follow-up visit.

